6.14.2. Description of Analyses

For the first interim analyses, only some key safety parameters described in the prior section will be examined and summarized.

The second interim analysis will include the MMRM analyses for HbA1c change from baseline, and body weight change from baseline. In addition to the safety parameters summarized for the first interim, ECG data will also be analyzed.

6.15. Clinical Trial Registry Analyses

Additional analyses will be performed for the purpose of fulfilling the Clinical Trial Registry (CTR) requirements. For CTR analyses, an AE will be considered 'Serious' whether or not it is a TEAE. An AE will be considered to be in the 'Other' category if it is both a TEAE and not serious.

Analyses provided for the CTR requirements include the following:

- Summary of AEs, provided as a dataset which will be converted to an XML file. Both Serious AEs and 'Other' AEs will be summarized by treatment group and by MedDRA Preferred Term (PT).
- For each Serious AE and 'Other' AE, for each PT and treatment group, the following will be provided:
 - o the number of participants at risk of an event
 - o the number of participants who experienced each event PT
 - o the number of events experienced.

Consistent with ClinicalTrials.gov (National Institutes of Health [NIH] [WWW]) requirements, a threshold (at a maximum of 5%) for frequency of 'Other' AEs can be implemented rather than presenting all 'Other' AEs. The determination of a threshold will be based on the overall number of 'Other' AEs.

7. Unblinding Plan

The purpose of the unblinding plan is to detail the procedures that are in place to minimize bias while preparing for or conducting any summary or analysis of the data for AC reports, data reviews, dose selection (interim efficacy/safety only), and developing/refining exposure analyses. Additionally, this plan identifies personnel who will be unblinded during the study, including unblinding for the AC interim analyses in support of the AC meetings.

The access to subject treatment assignments will not be provided to the investigator and site personnel until DBL is authorized for the planned final analysis at the completion of the blinded study.

The access to subject treatment assignments will not be provided to the following personnel until the primary data lock is authorized for the third interim analysis at the completion of the treatment period:

- Lilly personnel with direct site contact
- Lilly personnel responsible for data entry and data validation
- Lilly study team not in the AC and/or SAC.

After DBL, the study team will be unblinded to the study data to prepare for the analyses for CSR. Investigators can be provided treatment assignments for their subjects when unblinding has occurred and the information will not impact scientific integrity or introduce bias after final DBL.

7.1. Operational Procedures

The randomization code (treatment assignment) will be stored in the Lilly IWRS and will not be accessible to the blinded Lilly study team, except for those pre-specified in the unblinding plan to be unblinded, until the final DBL. Members from the SAC, AC, and the study global patient safety (GPS) scientist may be unblinded to data prior to the DBL. The SAC, composed of Lilly or Lilly designated third party organization (TPO) unblinded statistics personnel, PK/PD scientists and the PK/PD analysts (for efficacy/safety interim analysis only) will form a separate team from the Lilly blinded team. The SAC will obtain the randomization code from the unblinded data movement group in order to generate unblinded tables, figures, and listings (TFLs) for the AC. Membership is listed in Table 7.1 for each of the groups mentioned above.

Group Name	Group Members
Blinded Lilly study team	Lilly clinical study team personnel who work on the study and have
	direct site contact including the clinical research physician, CTM, data
	sciences and solutions, GPS personnel, and study monitors, etc, and non-
	site direct contact regulatory scientist, statistician(s). However, per Lilly
	procedure, for patient safety, the study GPS scientist will be unblinded to
	SAE patient-level data for patient safety.
Blinded Lilly statistics group	Lilly statisticians and statistical analyst(s)
SAC (unblinded)	Lilly statisticians and statistical analyst(s) or TPO statistical analysts
Unblinded PK/PD team scientists (part	Lilly study team PK/PD scientists and analyst(s), etc.
of the SAC)	
Assessment Committee	Lilly physicians, statisticians, and GPS personnel
Unblinded data movement group	Unblinded data movement representative
The program senior management	Lilly GIP/GLP senior medical director or above

Table 7.1. Study I8F-MC-GPGB Group Name and Membership

Abbreviations: CTM = clinical trial manager; GIP/GLP = glucose-dependent insulinotropic peptide/glucagon-like peptide; GPS = global patient safety; PK/PD = pharmacokinetics/ pharmacodynamics; SAC = Statistical Analysis Center; SAE = serious adverse event; TPO = third party organization.

More specifically, the data movement group will load CRF data, clinical laboratory results, ECG, and IWRS data into the designed blinded and unblinded locations. The blinded version of the data will then be provided to the blinded Lilly study team. The unblinded data will be provided to the SAC. The data movement group is not blinded, but is not involved in study-level activities

Periodically throughout the trial until the DBL, blinded data will be transferred by data movement per the data transfer plan to the blinded Lilly study team members including the blinded Lilly statistics group for the purpose of preparing Study Data Tabulation Model (SDTM) and Analysis Data Model (ADaM) dataset, AC reports, trial-level safety review (TLSR) reports, blinded AC reviews, TFL reviews, and CSR preparation. To minimize bias during statistical planning and data review, these transfers will be provided under the guidelines described in the following sections.

By setting up appropriate access privileges, the Lilly system will only allow unblinded personnel (unblinded statistician and/or programmers) to access data that contains unblinding information.

7.2. Site-Level Unblinding

The procedure for site personnel to unblind an individual patient's treatment assignment for an emergency is described in the protocol Section 7.3. Emergency unblinding for AEs may be performed by accessing the IWRS at the site level. When an IWRS Clinical Trial Study Management System (CT-SMS) is used to unblind a patient's treatment assignment, the computer application will maintain the date, reason for unblinding, and the identification of the person unblinding the treatment assignment. All calls resulting in an unblinding event are recorded and reported by the IWRS.

The site monitor is responsible for verifying compliance with the blinding procedures at the investigative site and verifying that access to the patients' treatment assignments remains restricted from the investigator and site personnel in direct contact with patients.

The investigator and site personnel are instructed to make every attempt to contact Lilly personnel when a patient's treatment assignment is unblinded at the site. The affiliate personnel document the unblinding records and inform the designated study team member, CTM, who documents the overall unblinding records for the entire study. The documentation is filed in the study files. A final Study Unblinding Summary will be prepared at the end of the study (at the study closeout).

7.3. Trial-Level Safety Reviews

Periodic TLSR summaries and listings will be produced by the blinded Lilly statistics group and delivered to the blinded Lilly study teams. These summaries will be blinded until after the DBL. They will contain neither randomization assignments nor postrandomization primary endpoint HbA1c, dose information, or PK data with the potential to unblind. Blinding flags will be created in the central laboratory database, based upon the Alert and Blinding Criteria document maintained by the Clinical Laboratory Operations (CLO) group. These flags will blind specific report data to the site and investigators. Data transferred to and exported from the clinical laboratory results will not be blinded to the Lilly team or to the data management of TPO performing the labs.

The complete list of TLSR variables include overall AEs, SAEs, TEAEs, AESIs, laboratory data, vital signs, discontinuations, concomitant medications.

7.4. Assessment Committee Reports

The blinded Lilly study team will remain blinded to randomization assignments and potentially unblinding results until after the DBL.

The SAC statistician is responsible for authorizing the access of Lilly personnel to unblinded data. Every attempt should be made to contact the statistician and document the authorization before access is given to unblinded data. A designated IWRS representative, data movement team or the replacement or their designee, will provide all data transfers to the Lilly statistics group based on the data transfer plan.

The study project statistician will be responsible for keeping a running log of individuals given access to any unblinded study data. This log will include the person's name, title, date of unblinding, level of unblinding (that is, group or patient), and purpose of unblinding. This record will be stored in a secure area and will be stored in eTFM via the study CTM after DBL.

7.4.1. Interim Reports

The first interim will be safety only reviews. The second interim will include key efficacy and safety. Due to data availability, PK/PD analyses will be performed at a later time.

7.4.1.1. First Interim

The following personnel will be unblinded to the first interim data, in order to perform the data analysis, prepare the AC reports, and review/discuss the results:

- ☑ The AC (determined in AC Charter)
- ✓ SAC (Lilly or TPO study personnel)✓ Computational Statisticians
- ☑ Others: No, but can be added upon AC Chair's request

7.4.1.2. Second Interim

For the second interim or PK/PD analyses, the following personnel will be unblinded to the PK-related data in order to develop the PK/PD modeling and/or TFLs:

- ☐ The AC (determined in AC Charter)
- ✓ SAC (Lilly or TPO study personnel)✓ Computational Statisticians
- ✓ Internal Pharmacokinetic Analysis Group (Lilly study personnel, part of the SAC)
 ✓ Pharmacokineticist and Pharmacokinetics Analysts

7.4.1.3. Reports Delivery

The following personnel will be unblinded to the efficacy, safety, and PK data, in order to perform data analysis, prepare the interim reports, review the results, and discuss business related matters:

- ✓ AC (determined in AC Charter)
- ✓ SAC (Lilly personnel) or its delegate✓ Computational Statisticians
- ☑ Internal Pharmacokinetic Analysis Group (Lilly personnel, part of SAC) or its delegate
 - ☑ Pharmacokineticist and Pharmacokinetics Analysts
- ☑ Others: Others who don't have direct site contact may be granted access to the results with approval of program team leader.

If PK reports needs more time to be generated, this interim reviews can be proceeded without PK data. A subsequent PK results review can be formed later after the results are available.

In addition, in order to perform the critical business development and the regulatory interactions, some personnel need to be unblinded to the related summary (group) level data, and possibly limited patient-level data after the interim safety/efficacy analysis. This unblinding requires approval from AC and signature for Confidentiality Responsibilities Agreement. The SAC statistician should be informed by AC Chair for documentation purpose.

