7.4.1.2. Second Interim	
7.4.1.3. Reports Delivery	45
7.4.2. Primary Lock (Third Interim)	46
7.5. End of Study Unblinding	46
8. References	47
9. Appendices	
/ · · · · · · · · · · · · · · · · · · ·	

Table of Contents

Table		Page
Table 5.1.	Dose-Response Assumption Used in Sample Size Determination.	13
Table 6.1.	Analysis Populations	16
Table 6.2.	Dose Strength Parameters and Corresponding Dose Strengths	20
Table 6.3.	Summary of Analyses for Primary Outcome	22
Table 6.4.	Vital Sign Summary Categories	24
Table 6.5.	Electrocardiogram Abnormal Categories.	31
Table 6.6	Sample Anti-Drug Antibodies (ADA) Assay Results	36
Table 6.7.	Sample Clinical Anti-Drug Antibodies (ADA) Interpretation Results	36
Table 6.8.	Adverse Events for Analysis with Immunogenicity Results	37
Table 7.1.	Study I8F-MC-GPGB Group Name and Membership	43

	Table of Contents	
Figure		Page
Figure 5.1.	Study design for I8F-MC-GPGB.	11

Page 6

I8F-MC-GPGB Statistical Analysis Plan Version 3

Table of Contents

Appendix		Page
Appendix 1.	Protocol GPGB Study Schedule (Schedule of Events)	49
Appendix 2.	Protocol GPGB Illustration of PK Sampling Schedule	55
Appendix 3.	Important Protocol Deviations	57

3. Revision History

The Statistical Analysis Plan (SAP) Version 1 was approved prior to first production data transfer.

The second version is approved before the first interim analysis. The following changes are made for the second version:

- 1. The second interim analysis time is changed from 100% patients finishing 16 weeks of treatment to 90% patients finishing 12 weeks of treatment.
- 2. A titrated dose integrated two-component prediction (ITP) model is added for the dose response analyses.

The third version is approved before the primary database lock. The following changes are made for the third version:

- 1. Clarify analyses datasets. Analysis dataset for modified intent-to-treat (mITT) population, excluding data after study drug discontinuation or rescue drug initiation, is added for the efficacy analyses to better reflect the study treatment effect.
- 2. Add a missing data imputation analysis for HbA1c and body weight.
- 3. Delete country from the statistical analyses that was accidently included as a strata factor. Delete visit window.

4. Study Objectives

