6.8. Protocol Deviations

Important protocol deviations will be listed for all randomized patients and summarized by treatment group. A list of important protocol deviation criteria for patients from the trial issues management plan is given in Appendix 3. Patients who deviate from the protocol in ways that would possibly affect efficacy results are going to be excluded from the per protocol analyses. That information can be found in Appendix 3. Patients meeting criteria for important protocol deviations will be identified either by statistical programming or based off of study monitoring that maintained by the study clinical trial manager (CTM). The final list of important protocol deviations will be reviewed and documented in the Important Protocol Deviations document by the study team prior to the primary outcome DBL.

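### The open access line in SAP 7.4.1.3 can, as worded, give interim efficacy results to members of the blinded team whom SAP 7.4 and 6.14.1 keep blind until the lock

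*SAP*

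**What the plan says.** SAP 7.4.1.3 introduces its distribution list for interim reports with "The following personnel will be unblinded to the efficacy, safety, and PK data". It names the Assessment Committee (AC), the Statistical Analysis Center (SAC) with its computational statisticians, and the internal PK group. It closes with an open category: "Others who don't have direct site contact may be granted access to the results with approval of program team leader". A later paragraph of the same section, on business development and regulatory contacts, sets tighter conditions: "This unblinding requires approval from AC and signature for Confidentiality Responsibilities Agreement".

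The parent section, SAP 7.4, states: "The blinded Lilly study team will remain blinded to randomization assignments and potentially unblinding results until after the DBL". It adds: "The SAC statistician is responsible for authorizing the access of Lilly personnel to unblinded data". It also has the study project statistician keep a log of everyone given unblinded data. SAP 6.14.1 likewise withholds unblinding information from the blinded team, and describes access before the lock as being for individuals identified in advance.

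Table 7.1 (SAP 7.1) defines the Blinded Lilly study team. After the members who deal with sites, the entry continues, directly after the prefix non-, "site direct contact regulatory scientist, statistician(s"; that is, a regulatory scientist and one or more statisticians without site contact. A separate Blinded Lilly statistics group holds statisticians and analysts, with no site role stated.

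Two deadlines matter. The Revision History (SAP Section 3) says "The third version is approved before the primary database lock". SAP 6.8 has the final list of important deviations "reviewed and documented in the Important Protocol Deviations document by the study team prior to the primary outcome DBL".

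**The concern.** Lack of site contact is a sensible test for protecting trial conduct at the sites. It does not protect analysis decisions, because the people who make those decisions are largely the ones without site contact. As worded, the open line lets the blinded statisticians see arm-level HbA1c and weight results while the SAP can still be revised and the deviation list is not yet final. If that happened, the sponsor could not show that those later choices were made without knowledge of the results.

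The approver adds to the difficulty. The program team leader does not appear in Table 7.1, so that role's own blinding status is undefined. The open line mentions neither the SAC statistician nor a confidentiality agreement.

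**Working it through.** The plan gives no figure of its own for this point. The check is mainly a comparison of passages, with two small calculations for scale.

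1. **Who qualifies under 7.4.1.3.** The conditions are no direct site contact and the program team leader's approval. The line has no exception for the blinded groups. The regulatory scientist and statisticians in the last part of the Table 7.1 entry meet the first condition by the table's own description.

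2. **Who must stay blind.** SAP 7.4 covers the whole Blinded Lilly study team, for treatment assignments and for results that could unblind. SAP 6.14.1 agrees. Section 7 withholds assignments from study team members outside the AC and SAC until the primary lock. The same people are therefore eligible in step 1 and barred in step 2.

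3. **Which rule prevails.** No sentence says. SAP 7.1 keeps the randomization code from the blinded team except for those pre-specified in the unblinding plan. Section 7.4.1.3 is part of that plan, so the open line could be read as such an exception. An unnamed category is hard to call pre-specified, so the opposite reading is also available. The text does not settle it.

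4. **Who approves.** SAP 7.4: the SAC statistician. SAP 7.4.1.3, open line: the program team leader. SAP 7.4.1.3, business and regulatory route: the AC, with a signed agreement. SAP 7.4.1.1, first interim, safety only: others are excluded unless the AC Chair asks. The interim that carries efficacy therefore has the looser line.

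5. **How much the second interim shows.** It includes MMRM results for HbA1c and weight (SAP 6.14.2).
   - Patients: 0.90 × 300 = 270, or 270 / 6 = 45 per arm.
   - The plan's SD of 1.0% is for Week 26; I assume the same at Week 12. Standard error of a difference between two arms = 1.0 × √(2/45) = 0.21 points; 95% half-width = 1.96 × 0.21 = 0.41.
   - If the SD is 20% lower or higher, the half-width is 0.33 or 0.50.
   - The planned Week 26 differences from placebo run from 0.74 to 1.44 points. The top three doses differ from one another by at most 1.44 − 1.17 = 0.27. If Week 12 effects were of similar size, a reader would learn a good deal about each dose against placebo and little about the ordering of the top doses.
   - The patient who brings the count to 90% still has 26 − 12 = 14 weeks of treatment left, so the final data are not yet in.

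6. **Which choices are exposed, and what they affect.**
   - *Version 3 data sets.* The on-treatment-without-rescue set is the default for efficacy analyses other than the primary one (SAP 6.9). Both restrictions were already in the Protocol: rescue in 10.3.1, study drug discontinuation in 8.1.2.
   - *Version 3 imputation analysis.* A sensitivity analysis for HbA1c and weight that fills gaps from the placebo arm (SAP 6.9.2.3).
   - *Titration ITP model.* It was added in version 2, approved before the first interim; whether to use it is left to the data (SAP 6.9.1.1). It enters the primary analysis only through imputed Week 26 values. At the planned 10% dropout that is 0.10 × 50 = 5 patients per arm, or 10 of 100 in the 10-mg and 15-mg arms. Values excluded after rescue would add to this.
   - *Alternative weight dose-response models.* A secondary endpoint (SAP 6.9.2.1).
   - *Deviation list.* It feeds the per-protocol set, which is supportive; Appendix 3 already marks which deviations exclude a patient.

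**The case against.** The strongest reply is that the open line sits under SAP 7.4, whose general rule keeps the blinded team blind, so the extra people must come from outside that team. Table 7.1 lists a program senior management group that would fit. Access is discretionary, and SAP 7.1 adds system controls. The approver rules can also be reconciled in part: the AC Chair rule belongs to the first interim, the AC-plus-agreement rule to a specific use, and the SAC statistician's authorization could apply on top of both. The log covers any unblinded study data. The Protocol (10.3.7) allows interim detail to sit in an AC charter, which is not among the documents. Finally, this is a Phase 2 trial with no stopping for efficacy or futility, and the first two interims serve internal decisions.

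Much of this stands. It narrows the approver conflict to the program team leader against the SAC statistician, and it lowers the stakes. It does not remove the overlap in steps 1 to 3: 7.4.1.3 neither limits the category to senior management nor refers back to 7.4. A log records access after the fact but does not keep a person who has seen results away from later analysis decisions. The absence of stopping rules does not help either, since the exposure lies in analysis choices.

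**Conclusion.** The plan contains an internal conflict: its access line can reach people whom it elsewhere keeps blind, on the approval of someone other than the authorizing statistician. It is worth correcting. The consequences are limited, because the exposed choices mostly concern supportive or secondary analyses.

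Three stronger readings go beyond the documents:

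- A reader might infer that blinded statisticians did see interim results, or that version 3 was written with them in view. Nothing shows that anyone in the blinded groups was given access, and the second interim is not dated relative to version 3. The point concerns what the plan permits.
- A reader might infer that pre-specification of the primary analysis has failed. The titration model predates the first interim, and its effect on the primary result runs only through missing Week 26 values.
- A reader might attach an inflated error rate, for example from taking the better of two correlated analyses. That calculation supposes that both final results are visible when the choice is made, whereas the interim gives Week 12 data. It also needs correlations that the documents do not give. The success rule itself, any one of four doses beyond −0.8% without multiplicity adjustment, does not protect a trial-wide 10% rate. No such figure should be quoted.

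The precision figures in step 5 assume equal arms, 300 randomized and a Week 12 SD near 1.0%. The conflict itself depends on none of these.

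**What to change.** Reword the last item of the list in SAP 7.4.1.3 along these lines: *Others outside the Blinded Lilly study team and the Blinded Lilly statistics group (Table 7.1), and not involved in writing or approving the SAP or the deviation list before the primary lock, may be granted access with prior documented authorization by the SAC statistician per Section 7.4, a signed confidentiality agreement and an entry in the access log.*

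This removes the overlap with Table 7.1, gives the route one authorizing role consistent with 7.4, and brings its confidentiality condition into line with the business and regulatory route.

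The cost is a change of SAP wording, with no effect on sample size, data collection or analysis. The downside is practical: anyone on the blinded team who is needed for regulatory or business work at the interim must leave that team first.
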